Futility Interim Analysis Plan. This randomized, double-blind study adopts an adaptive design with a single pre-specified, planned, unblinded interim analysis for futility stopping based on conditional power (CP) (stochastic curtailing method) (Halperin et al., 1982; Lan et al., 1982) or an equivalent stopping boundary on interim Z-test value (B-value) (Lan and Witts, 1988). The purposes of this formal interim analysis are to assess CP levels which are the probability of reaching statistically significant treatment difference at study end given the interim results. To avoid inflation of Type I error, no early stopping for efficacy is planned in this study. The unblinded data will be only available to external statistician [name] and not the PIs or other study staff.

It is well known that futility termination will reduce the Type I error rate (alpha) and inflate the Type II error rate (beta =1 minus power of the test), with the level of beta inflation bounded by P_{L0} , the probability of stopping for futility under the null hypothesis of no treatment effect (Lan et al., 1982; Lachin 2005). In order to maintain the design Type I error rate (alpha) at 5% and power close to 85%, we use an iterative procedure to determine the CP utility boundary values and the adjusted Z-test critical value in the final analysis, with 60% (P_{L0}) chance of stopping for futility under the null hypothesis. This provides: 1) a CP futility stopping boundary value equal to 0.3 at 50% enrollment (i.e. stop the trial if CP observed < 0.3) under the original design assumption (see Sample Size Calculation), 2) an adjusted Z-test critical value of 1.947 (ZF) for declaring significant treatment effect in the final analysis (or $P \le 0.0515$), and 3) an overall power of 84.6%, i.e. 15.4% overall Type II error rate with 3.1% false negative error rate at interim look and 12.3% probability of continuing the trial and failing to reject the null hypothesis (false negative error rate) at study end.

In summary, we provide the following futility stopping rule for assessing interim results at 50% enrollment:

- 1. A recommendation to stop the trial for futility if CP value for comparing combined oxytocin vs. placebo (i.e. the probability that final study results will be statistically significant given interim data) is less than 30% under the original design assumption. An equivalent boundary for interim Z-test value is 0.253 (interim P>0.800), interim B-value ≤ 0.179, or if equivalently interim drift parameter estimate ≤ 0.358.
 - a. If futility stopping criteria are met for the combined oxytocin group, we will examine CP and interim Z-test value for each dose (vs. placebo) to check if both dose groups meet a similar stopping criterion CP <0.3 (or P>0.800) for an overall alpha of 5% and an adjusted power of 80%.
 - b. In case of dropping only 1 dose arm and reallocation of remaining subjects to another arm we will use a fixed weighted Z-test method to protect the Type 1 error (Cui et al., 1999; Lan et al., 2005).
- 2. To declare the treatment effect significant if p-value computed at study end (N=72) is less than 0.0515.

This futility interim monitoring plan will include a vigorous data quality control to ensure successful signal detection in potential treatment effects. In addition to verifying validity of study design assumptions using the unblinded interim data, we will perform blinded, ongoing assessments of inconsistencies in the efficacy outcome measures, inter-relationships between efficacy variables, missing data patterns, and will implement a data management plan that has real-time capability to detect, query, and address data issues in the study.

Analysis Methods: The primary population for efficacy analyses includes all randomized subjects based on the intention-to-treat principle. The population for safety analyses will include all subjects who receive at least one dose of study medication. In the primary analysis, we test the hypothesis of difference in PANSS total change score (Week 6) between the combined oxytocin and placebo groups with adjustment for baseline score using a likelihood-based mixed-effects model for longitudinal data analysis (MMRM LDA) (Fitzmaurice and Ware, 2004). The MMRM LDA model can accommodate incomplete data under the assumption of ignorable attrition (see below under Missing Data). The same MMRM LDA model will be applied to evaluate the dose-response relationship using a linear contrast for the placebo and oxytocin dose groups, comparisons of treatment groups over time using treatment-by-visit (categorical visit variable) interaction term, and the trajectories of treatment responses over time based on time slope computed for each subject (continuous time variable).

Secondary efficacy measures will be the PANSS positive symptom and negative symptom subscales, PANSS general psychopathology subscale, CGI-S, CGI-I HAM-A, CCDS, GAF, cognitive scales as with the primary endpoint using the same MMRM LDA analyses. No multiplicity adjustment will be made in the secondary analyses. Appropriate descriptive statistics with 95% confidence intervals will be provided within and across treatment groups. Normal assumption will be checked and nonparametric alternatives will be considered if the assumption is seriously violated.

Mediators and baseline moderators of treatment effects on efficacy outcome measures will also be explored (Kraemer et al., 2006). The significance of moderator effects due to baseline characteristics (age, gender, initial

PANSS scores, duration of illness, class of medication) will be tested using treatment-by-baseline characteristic interaction terms in the MMRM LDA and/or ANCOVA models. To assess impact of improvement in one domain (e.g. positive symptoms) on the efficacy of a related symptom domain (e.g. negative symptoms), a mediator analysis model with terms for treatment, baseline, and positive symptoms improvement will be applied to determine significance of oxytocin effect on reductions in negative symptoms after adjustment for potential positive symptom improvement. We will perform similar mediator analysis for assessing inter-relationships between cognitive improvement and symptom improvement in positive and/or negative symptoms. In addition, cross-sectional baseline and longitudinal change score associations between treatment outcome measures and mediator effects will be assessed by including mediators as time-varying covariates in the MMRM LDA models (Diggle et al., 2001).

MU-Suppression. Data will be analyzed in two ways. Pearson rank correlations will be used to examine correlations between mu wave suppression in response to a single dose of OT and symptom severity at the end of 6 weeks of treatment. In additional exploratory analyses, mu suppression values will be split at the median into High suppressors and Low suppressors and followed up by correlations with symptom measures to determine if initial high suppression is correlated with greater improvement in symptom severity. Secondarily, Pearson rank correlations will be conducted between mu wave suppression and symptom severity at baseline, and between mu wave suppression and symptom severity after administration of a single dose of oxytocin.

Safety Endpoints. The safety dataset will contain all subjects who take at least one dose of oxytocin. All adverse events will be coded using the most current version of the Medical Dictionary for Regulatory Activities (MedDRA). The number and percentage of subjects reporting treatment-emergent adverse events will be tabulated within each dose group by treatment, system organ class (SOC) and MedDRA-preferred term. Treatment-emergent adverse events will be those adverse events that begin or worsened following the first dose of study drug. Adverse events will be further classified by severity and investigator-assigned relationship to study drug.

Clinical laboratory values and vital signs measured at the end of each treatment period will be analyzed using ANOVA, with factors sequence, period and treatment. Dose-response relationships will be explored and any laboratory values that fall outside normal ranges will be identified.

Missing Data. Some observations may be missing after baseline assessment. Individual missing items in all scales will not be imputed. All subjects expressing the desire to discontinue the study will be asked to come in for a final assessment, prior to stopping their medications. The primary analysis will be based on the likelihood based mixed-effects model (MMRM LDA) which provides valid estimates of treatment effect under the missing at random (MAR) assumption. The assumptions about random dropout and MAR can be tested using methods proposed by Diggle et al. (2001) and dropout cohort visualization as in Potkin et al, (2009). Two sensitivity analyses will be conducted to evaluate the robustness of results: one based on a mixed-effects model for missing not at random (MNAR) data with covariate adjustment for dropout measures (Wu and Follmann, 1999; Wu et al., 2001), and the other based on the usual LOCF-ANCOVA method with missing data following dropout imputed by an individual's last observed measurement. Further details are provided in the Statistical Analysis Plan, which will clearly specify the mixed-effects model methodology, sensitivity analyses, and evaluation of the assumptions.

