9. RESEARCH DESIGN AND METHODS

OVERVIEW:

The proposed study is a randomized, double-blind, placebo-controlled study of the value of adjunctive intranasal oxytocin added to existing antipsychotic treatment compared with adjunctive placebo in subjects with schizophrenia. Enrolled subjects will be randomized and receive 6 weeks of treatment with one of the following adjunctives to a stable antipsychotic regimen: 1) intranasal oxytocin (84 IU/day), intranasal oxytocin (168 IU/day) or intranasal placebo. The study will be conducted over 2 years. Approximately seventy-one subjects will be entered into the study, on average 35/36 at each site each year.

PRIMARY OUTCOME MEASURE:

Positive and Negative Syndrome Scale (PANSS): The three subscales of the PANSS include the Positive scale (7 items), the Negative scale (7 items), and the General Psychopathology scale (16 items). The total PANSS score is the sum of all 30 items of which each item is scored on a 1-7 rating system (7 indicating the worst symptoms). The items on the PANSS focus on symptoms that are common in patients with psychotic disorders and include hallucinations, delusions and disorganization as well as mood disturbances.

SECONDARY OUTCOME MEASURES WILL INCLUDE:

Global Assessment of Functioning (GAF): The GAF considers psychological, social, and occupational functioning on a hypothetical continuum of mental health illness. Scores on the GAF range from 1 (extremely severe) to 100 (superior functioning).

Clinical Global Impression-Severity of Illness (CGI-S): The CGI-S is used to evaluate changes in overall severity of illness. Scores range from 1 (not at all) to 7 (among the most extremely ill).

Clinical Global Impression-Global Improvement (CGI-I): The CGI-I is a global assessment to evaluate the subject's improvement or worsening from baseline. Scores on the CGI-I scale range from 1 (very much improved) to 7 (very much worse)

Calgary Depression Scale for Schizophrenia (CDSS) is a ten item diagnostic questionnaire intended to assess the severity of depression symptoms experienced by a given patient. The CDSS will be administered by a trained and qualified rater at each scheduled study visit.

Hamilton-Anxiety Scale (HAM-A): The HAM-A is a clinician administered scale for the evaluation of anxiety symptoms. The HAM-A consists of 14 items of which each item is scored 0 (not present) to 4 (very severe).

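### One blank PANSS item voids the visit's primary total, because the total needs all 30 items and the plan imputes none; the cost is precision, and a per-subscale proration rule would avoid most of it

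*Combined protocol and SAP*

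**What the plan says.** All of the relevant text is in section 9 of the combined protocol and SAP.

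- **Primary Outcome Measure.** "The total PANSS score is the sum of all 30 items of which each item is scored on a 1-7 rating system". The three subscales have 7 Positive, 7 Negative and 16 General Psychopathology items.
- **Statistical Consideration, Missing Data.** "Individual missing items in all scales will not be imputed". This is a positive rule covering every scale, so it excludes proration as well as more elaborate methods.
- **Same paragraph, on missing visits.** The mixed model is said to be one that "provides valid estimates of treatment effect under the missing at random (MAR) assumption". One sensitivity analysis is LOCF-ANCOVA, with "missing data following dropout imputed by an individual's last observed measurement". Both deal with missing visits and dropout, not with items inside a visit that took place.
- **Same paragraph, on deferred detail.** "Further details are provided in the Statistical Analysis Plan, which will clearly specify the mixed-effects model methodology, sensitivity analyses, and evaluation of the assumptions". Item-level scoring is not on that list.
- **Futility Interim Analysis Plan.** The data management plan is to have "real-time capability to detect, query, and address data issues in the study".

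No sentence says what becomes of a total when an item is blank. There is no maximum number of missing items, and no statement that the total is then missing.

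**The concern.** The primary test is on the change in PANSS total at Week 6, in about 72 subjects. The total is long, so even a low blank rate per item becomes a noticeable rate of incomplete totals. Each incomplete total removes 29 ratings that were actually made at that visit. The mixed model can borrow from the subject's other visits, but it is fitted to totals and has no access to the items of the voided one.

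The plan also leaves the analyst to infer the consequence of a blank from two paragraphs that do not refer to each other. The scoring of a primary endpoint should be settled before anyone sees unblinded data.

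**Working it through.** **Inputs from the plan (section 9).** Items: 7 + 7 + 16 = 30, which agrees with the stated 30. Each item is scored 1 to 7, so a complete total lies between 30 and 210. Correlation 0.5 with an AR(1) structure and a target effect of 0.3 SD come from Sample Size Calculation; N = 72.

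**Assumed inputs.** The blank rate per item, p, is not in the documents; I use 0.1%, 0.5% and 1%, with blanks independent. The SD of the PANSS total is not given either.

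**Step 1: what the two rules imply.** A score requiring all 30 items, with no imputation allowed, does not exist when 29 are present. The total for that visit is therefore missing.

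**Step 2: share of totals lost.** f = 1 − (1 − p)^30.

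| p | f |
|---|---|
| 0.1% | 1 − 0.999^30 = 3.0% |
| 0.5% | 1 − 0.995^30 = 14.0% |
| 1% | 1 − 0.99^30 = 26.0% |

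**Step 3: loss of Week 6 information after the model borrows from Week 5.** With correlation ρ = 0.5 between adjacent visits, the variance of the Week 6 mean rises by the factor (1 − ρ²)/(1 − f) + ρ², and the information lost is 1 minus its reciprocal.

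| p | Variance factor | Information lost | Equivalent of 72 |
|---|---|---|---|
| 0.1% | 0.75/0.970 + 0.25 = 1.023 | 2.2% | 1.6 |
| 0.5% | 0.75/0.860 + 0.25 = 1.122 | 10.8% | 7.8 |
| 1% | 0.75/0.740 + 0.25 = 1.264 | 20.9% | 15.0 |

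This takes Week 5 as observed; blanks there too make the loss slightly larger. For the time-averaged effect used in the sample size calculation, the same AR(1) structure over six visits gives smaller losses: under 1% at p = 0.1% and about 4.6% at p = 0.5%.

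**Step 4: what a per-subscale limit would recover.** Allow 1 blank of 7 Positive, 1 of 7 Negative and 2 of 16 General. A total is then lost with probability 1 − P(X₇ ≤ 1)² × P(X₁₆ ≤ 2), where X is binomial with rate p.

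- p = 0.1%: 0.004%
- p = 0.5%: P(X₇ > 1) = 0.052%, P(X₁₆ > 2) = 0.007%; total 2 × 0.052% + 0.007% ≈ 0.11%
- p = 1%: P(X₇ > 1) = 0.203%, P(X₁₆ > 2) = 0.051%; total ≈ 0.46%

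**Step 5: if observed items were summed regardless.** The total would fall by the unrated item's score, 1 to 7 points. On average that is 55/30 = 1.8 points at the entry minimum of 55 and 90/30 = 3.0 points at the stratification cut of 90. The mean shift over an arm is 30 × p × (total/30) = p × total. At p = 0.5% and a total of 90 that is 0.45 points, in every arm if blanks are equally common. If the SD is 15 to 20 points (assumed), the target effect is 4.5 to 6 points.

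**The case against.** The strongest objection is that the documents already imply a coherent rule. No complete set of items means no total, and a likelihood-based model then handles the missing visit under MAR. Declining to impute is a legitimate choice. PANSS is a clinician-administered structured interview and real-time queries are promised, so blanks may be rare. At 0.1% per item the Week 6 loss is about 2%. Independence also matters: if blanks cluster within interviews, fewer totals are affected at the same rate, and proration rescues fewer of them.

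Most of this stands, and it limits the size of the point. It does not remove it. Queries can reduce blanks but do not say how to score those that remain, and a symptom not rated at interview may not be recoverable later.

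A reader might infer three stronger claims that the documents do not support.

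- **Blanks would bias the primary result toward improvement.** A sum of 29 items is not the score the plan defines, and scoring a blank as 0 would insert a value below the scale's minimum. Even if it were done, blanks equally common in all arms of a double-blind trial would largely cancel between arms, and a baseline blank would look like later worsening. Differential blanks would be needed.
- **Incomplete baseline totals breach the all-randomised population** ("The primary population for efficacy analyses includes all randomized subjects based on the intention-to-treat principle"). The study procedures require PANSS at baseline, and its score is needed for the entry minimum and the randomisation stratum. A blank there would probably be noticed and completed before randomisation.
- **Every scale is defined as a full sum.** Only the PANSS total is. The no-imputation rule does cover all scales, but the other scoring definitions are not given in that form.

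Nor are the 29 ratings lost from every analysis: subscales without the blank still enter the secondary analyses.

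**Conclusion.** The point holds as a matter of precision and specification. The definition of the total and the no-imputation rule together void a visit's primary score for one blank item, and nothing else in the plan recovers the remaining 29 ratings. Under independent blanks at assumed rates of 0.1%, 0.5% and 1% per item, about 3%, 14% and 26% of totals are lost. The corresponding loss of Week 6 information is about 2%, 11% and 21%, given the plan's correlation of 0.5. The true rate is unknown and may well lie at the low end. No bias in the treatment effect is shown. It remains a possibility only because no sentence forbids summing fewer than 30 items. This is a cheap improvement, not a flaw that threatens the trial's conclusions.

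**What to change.** Replace the no-imputation sentence in Missing Data, before unblinding, with:

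> *A missing PANSS item is replaced by the mean of that subject's observed items in the same subscale at that visit, provided that no more than 1 of 7 Positive, 1 of 7 Negative and 2 of 16 General items are missing. Otherwise that subscale and the total are set to missing. Totals are never formed by summing fewer items.*

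The limit should be set per subscale. A single limit of 10% of the 30 items would allow 3 of 7 Positive items to be filled from the other four, while 10% of a 7-item subscale allows none. State a similar limit, per scale or per subscale, for the other multi-item scales. Repeat the primary analysis on complete totals only.

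The cost is a short paragraph and a few lines of code. The downside is a mild assumption that a blank item resembles the subject's other items in that subscale, which the complete-totals analysis checks. If the sponsor prefers to keep the no-imputation rule, the plan should at least say that a total with any missing item is itself missing; that removes the ambiguity but not the loss of data.

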Specific Aim #3:Establish the time needed to reach peak efficacy. Duration of treatment in the original study was three weeks, and significant therapeutic benefit was observed only at the three-week endpoint but not earlier. In the proposed study, subjects will receive study drug for 6 weeks and we expect that the size of the therapeutic benefit of oxytocin will increase from 3 to 6 weeks.

Specific Aim # 4: Investigate the possible cognitive effects of intranasal oxytocin. In the pilot study, oxytocin significantly improved short term recall performance in the California Verbal Learning Test. This raises the possibility that chronic oxytocin will improve cognitive deficits associated with schizophrenia. This study will test this hypothesis using the Computerized Multiphasic Interactive Neurocognitive DualDisplay™ System (CMINDS®) and Mayer-Salovey-Caruso Emotional Intelligence Test: Managing Emotions (MSCEIT™ ME).

Specific Aim #5: To determine if daily intranasal oxytocin is sufficiently safe, feasible and acceptable to patients to warrant further clinical development. Information derived from this study will inform development of oxytocin not only for schizophrenia but other potential neuropsychiatric disorders.

Specific Aim #6: The objective of the study is to compare the efficacy of intranasal oxytocin versus intranasal placebo to improve symptoms in schizophrenia patients who have residual symptoms despite being on adequate treatment with antipsychotic medication. Improvement will be measured by total score in the Positive and Negative Syndrome Scale (PANSS).

Specific Aim #7: To determine if oxytocin-induced enhancement of mu-rhythm suppression of 'mirror' neurons in schizophrenia patients can serve as a predictive biomarker of individual clinical response to this neurohormone.

Secondary objectives include:

 To evaluate the efficacy of intranasal Oxytocin as measured by change in the total CGI-Severity and Improvement scores

- To evaluate the efficacy of intranasal Oxytocin as measured by change in the total GAF score
- To evaluate the efficacy of intranasal Oxytocin as measured by change in the total scores of HAM-A.
- To evaluate the efficacy of intranasal Oxytocin on self-rated social anxiety as measured by change in the total Social Phobia Inventory (SPIN).
- To evaluate the efficacy of intranasal Oxytocin as measured by change in the total Calgary Depression Scale for Schizophrenia (CDSS) scores.

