Mu wave suppression paradigm: If subjects agree to participate in this sub-study, the informed consent for EEG collection will be obtained prior to any EEG procedures. EEG waves will be recorded over 32-sites using a standard 32-electrode cap with the Biosemi system (9), while subjects are watching 60-80 second videos. The videos will consist of experimental conditions (point light animations of biological and non-biological motion, scrambled condition) and baseline condition (2 moving balls). All videos will be presented twice, using Presentation software (10). Data from both trials will be combined prior to analysis. Filters will be set to automatically identify and block any segments with eye movements and body movements (using +/- 40 microvolt deviations). Data will only be analyzed if there is at least 2 minutes of clean EEG per condition. For each segment, integrated power in the 8–13 Hz range will be computed using a Fast Fourier Transform. Mu suppression will be calculated for central (C3, Cz and C4) and occipital (O1 and O2) sites using the equation: Mu suppression = log10 (mu power of experimental condition/ mu power of ball condition). Occipital site electrical discharges will be recorded, integrated for power and compared between groups to determine if posterior alpha activity is causing differences across conditions.

STUDY PROCEDURES

Visit	Screen	Baseline	Midweek	3	4	5	6	7	8/ET
Week	-1	0	0	1	2	3	4	5	6
Days	-7 to -1	0	3/4	7	14	21	28	35	42
General Procedures									
Informed Consent	Х								
Assess Inclusion/Exclusion	Х	Х		Χ	Х	Х	Х	Х	Х
Medical History	Х								
Physical Exam	Х								
SCID/Psychiatric History	Х								
Urine Drug Screen ^b	Х								
Urine Pregnancy Screen ^c	Х	Х							
Vital signs/ weight	Х	Х		Χ	Χ	Х	Х	Х	Х
Blood chemistryd/Urine osmolality	Х								Х
Oxytocin Levels ^e		XX							Х
EEG	XX								Х

Clinician-Rated Scales									
PANSS ^f	(x)	Х		Х	Х	Х	Х	Х	Х
HAM-A/ CDSS/ CGI:S ⁹ /									
CGI:I/ GAF		Х		Х	Χ	Х	Х	Х	Х
Cognitive tests (CMINDS® and									Х
MSCEIT [™] ME) ^h	Х	Х							
Patient-Rated Scales									
CTQ	Х								
TSQM		Х		Х	Х	Х	Х	Х	Х
PTS/ SPIN/ ASEX ⁱ /									
ER-40/ ECR		XX		Х	Х	Х	Х	Χ	Х
Other Procedures									
Mid-Week Safety Call ^j			Х						
Dispense study drug		Х		Х	Х	Х	Х	Х	
Single Challenge Dose ^k	Х								
Concomitant Meds		Х	Х	Х	Х	Х	Х	Х	Х
Adverse Events		Х	Х	Х	Х	Х	Χ	Х	Χ
1-hr safety monitoring following in-									
clinic dose		Х							

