h Practice improvement is expected with repetition of some MATRICS tests. While the parallel group design will determine any improvement beyond the practice effect, neuropsychologists [name] and [name] have pointed out the majority of practice effect occurs between the first and second administrations of the MATRICS battery (personal communications). This finding by [name] and [name] regarding paper versions of the MATRICS™ should translate to the computerized versions of the CMINDS® as O'Halloran et al. (2007) found that standard paper administration versions and computerized administration versions of neurocognitive assessment instruments are substantially equivalent. These computerized versions yielded highly equivalent measures of absolute agreement throughout all the test batteries when compared to the standard paper versions. The group comparison will be between baseline (after the majority of practice effect has occurred) and 6 weeks. While this strategy may miss transient improvement between these timepoints it will decrease the practice effect. Transient improvements in cognition are not clinically meaningful.

All patient-rated scales except the ASEX will also be given 50 minutes after the in-clinic dose at the Baseline Visit.

^jA Mid-Week Safety Call to Study Site - The subject will be instructed to contact study staff on day 3 or day 4 of taking study drug. This call will be a brief open ended question and answer discussion to find out the subject's experiences with the study medication over the past few days and answer any questions that may arise.

^kA challenge dose will be administered between screening EEG paradigms. This dose will only be administered after all other inclusion/exclusion criteria have been verified. All subjects will receive 24IU as a challenge dose.

Study Procedure Details

Visit 1 – Screening (approximately 4-5 hours)

During Visit 1 of the study the volunteer will:

- Be asked questions about medical and psychiatric history
- Participate in a clinical interview called a Structured Clinical Interview for DSM-IV-TR (SCID) which is a structured question and answer discussion. This will be performed by a trained study staff who will ask a series of questions about behaviors and mood symptoms over time
- Be given a physical examination by one of the study doctors
- Have weight, pulse and blood pressure measured

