- If the volunteer is a woman capable of having children, a urine test will be done to ensure she is not pregnant
- Give a urine sample for testing to make sure there are no illegal or controlled substances in his/her body. The results of any urine drug screen will remain confidential and be disclosed only as required by law
- Blood draw (about one teaspoon or 5 mL) and urine sample will be collected that will include standard tests to make sure volunteers are healthy
- Be asked questions about health and any current illnesses or medications (including over-the-counter medications, herbal remedies, alcohol consumption, and substances of abuse).
 Be asked a series of questions about how s/he was feeling within the past few weeks such as whether there were anxious feelings, feelings of depression or difficulty concentrating. The volunteer will also possibly be asked about symptoms that are commonly associated with schizophrenia using a clinical interview called the SCI-PANSS (Structured Clinical Interview Positive and Negative Syndrome Scale).

The SCI-PANSS will be completed at the discretion of the investigator if he feels that the subject may not met entry criteria

- Complete a series of activities which will be used to measure process of thought called the CMINDS® and MSCEIT™ ME
- Premenopausal women will be queried regarding their menstrual cycles and data correlated with clinical findings
- Once all inclusion/exclusion criteria have been met subjects will have a baseline EEG performed
- Subsequently subjects will receive a, one time, challenge dose of 24 or 48 IU oxytocin followed by the EEG paradigm

Visit 2-Baseline (approximately 2 hours)

During Visit 2 – Baseline, the volunteer will:

- Have weight, pulse and blood pressure measured
- Be asked questions about health and any current illnesses or medications (including over-the-counter medications, herbal remedies, alcohol consumption, and substances of abuse)
- Be asked a series of questions about how s/he was feeling within the past few weeks such as whether
 there were anxious feelings, feelings of depression or difficulty concentrating. The volunteer will also be
 asked about symptoms that are commonly associated with schizophrenia using a clinical interview called
 the SCI-PANSS (Structured Clinical Interview Positive and Negative Syndrome Scale)
- Complete a series of activities which will be used to measure process of thought called the CMINDS® and MSCEIT™ ME

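### The posterior-alpha check on mu suppression compares groups although its question is about conditions, and its result plays no part in the Aim 7 correlations

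*Combined protocol and SAP*

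**What the plan says.** Section 9, Mu wave suppression paradigm, takes the same frequency band at every site: "integrated power in the 8–13 Hz range will be computed using a Fast Fourier Transform". The index is a ratio of two conditions within one person, "Mu suppression = log10 (mu power of experimental condition/ mu power of ball condition", and it is formed at both sets of electrodes: "Mu suppression will be calculated for central (C3, Cz and C4) and occipital (O1 and O2) sites using the equation". Occipital power is then to be "compared between groups to determine if posterior alpha activity is causing differences across conditions". The paragraph does not say which groups are meant, or what follows if a difference is found.

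Aim 7 (Section 6) asks whether oxytocin-enhanced mu suppression "can serve as a predictive biomarker of individual clinical response to this neurohormone". Its analysis, under MU-Suppression in Statistical Consideration, consists of "correlations between mu wave suppression in response to a single dose of OT and symptom severity at the end of 6 weeks of treatment". That text names no electrode site, occipital covariate, exclusion or decision rule. It adds an exploratory median split into high and low suppressors.

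The single-dose recordings are made at screening, before and after the challenge dose. Randomisation follows at Visit 2, and EEG is repeated at Visit 8 or early termination. Footnote k to the procedures table states "All subjects will receive 24IU as a challenge dose", while the Visit 1 description has a "challenge dose of 24 or 48 IU oxytocin followed by the EEG paradigm".

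**The concern.** Central mu and posterior alpha share the 8–13 Hz band, and the plan itself recognises that posterior alpha might produce the condition differences. The check chosen for this contrasts people with people, whereas the suspected artefact is a change within a person between the experimental and ball videos. A change of that kind common to all arms leaves no trace in a comparison of arms. For the screening recordings, randomisation comes later, so the expected difference between arms is zero however strong the artefact is.

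What is at stake is how Aim 7 is interpreted. If occipital reactivity to the videos leaks into the central electrodes and also varies with symptoms, the planned correlation can reach significance without any mu-specific content. Nothing in the analysis text would show this.

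**Working it through.** The documents give no sample size, power or error rate for the EEG sub-study, so there is no stated figure to reproduce. The check sets the passages side by side and then illustrates the consequence with assumed inputs.

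**1. Question against test.** The question is whether occipital power differs between experimental and ball conditions. For subject i this is O_i = log10(occipital experimental power / occipital ball power), and the matching hypothesis is mean(O) = 0. A between-arm test instead examines mean(O | arm A) − mean(O | arm B). If every arm shifts by δ, that is δ − δ = 0 for any δ.

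**2. Simulation of that point.** Assumptions, none from the documents: n = 36 or 72 (72 being the whole planned trial, 24 placebo and 48 oxytocin), split 1:2; SD of O 0.15; δ = −0.05 or −0.10 in all arms; central index = mu + k × O with k = 0.3 or 0.7; no true mu suppression; outcome correlated 0.4 with O only; two-sided 0.05; 4,000 runs per scenario.

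| Test | n = 36 | n = 72 |
|---|---|---|
| Between arms, common shift | 4.6–5.4% | 4.6–5.4% |
| Across conditions, δ = −0.05 | 50% | 79% |
| Across conditions, δ = −0.10 | 97% | 100% |
| Between arms, shift differs by 0.05–0.10 | 15–45% | 26–76% |
| O by high/low suppressor split | 27–84% | 49–99% |
| Aim 7 correlation, unadjusted | 9.5–28% | 16–49% |
| Aim 7 correlation, O as covariate | 4–5% | 4–5% |

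The first row is the alpha level: the arm comparison does not see a common shift. The unadjusted false-positive rate hardly changes with δ (at n = 36 and k = 0.7 it is 28.2% for −0.05 and 28.0% for −0.10), because it depends on how O varies between people, not on its mean. The across-condition test and the covariate therefore do different jobs, and both are needed.

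**3. Size of a spurious correlation.** If the central index relates to symptoms only through O, then r(central, symptom) = r(central, O) × r(O, symptom). Assumed ranges are 0.3–0.7 and 0.2–0.4:
- 0.3 × 0.2 = 0.06
- 0.5 × 0.3 = 0.15
- 0.7 × 0.4 = 0.28

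The chance of significance by the Fisher approximation, with z = atanh(r) × √(n − 3) against ±1.96, is about 6%, 14% and 38% at n = 36, and 8%, 24% and 67% at n = 72.

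**4. Cost of adjusting.** Suppose instead that O1/O2 picks up true mu, with r(central, O) = 0.7 and a true r of 0.30. Then r(O, symptom) = 0.7 × 0.30 = 0.21, and the partial correlation is (0.30 − 0.7 × 0.21) / √[(1 − 0.49)(1 − 0.0441)] = 0.153 / 0.698 = 0.22. Power at n = 72 falls from 73% to 45%.

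**The case against.** Several stronger readings are tempting, and the documents do not support them.

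- *The check can detect nothing.* This is too broad, because the groups are undefined. Arms exist at Visit 8, where a comparison can show a shift that differs by arm, which is relevant to the secondary objective on whether oxytocin improves mu suppression. If the high/low suppressor split is meant, it is available from the screening data and can show person-level leakage.
- *No groups of any kind exist at screening.* No randomised groups do. But footnote k and the Visit 1 description disagree on the challenge dose, and two dose levels would create groups there. Comparing them would still not test the condition effect.
- *General alpha or arousal contaminates the index.* Alpha that scales power equally in both conditions cancels in the log ratio. Only condition-specific reactivity survives. The non-biological and scrambled videos are further potential controls, although the analysis text does not say how they enter.
- *The occipital index is never analysed.* The MU-Suppression text names no site, so it could be read as including O1/O2. The gap is under-specification: no site is named and no consequence stated.
- *The artefact is as large as the effect the study could detect.* For 80% power the correlation must be about 0.39 at n = 48 or 0.33 at n = 72. An r of 0.30 has 55% and 73% power. Participation in the EEG is optional, so n may be smaller still.

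It is also fair that this is a correlational sub-study within a pilot, and that adjustment can remove real signal. These points limit the finding and its weight. None of them makes a between-group comparison answer an across-condition question.

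**Conclusion.** The point holds in limited form. As written, the posterior-alpha check does not test its stated question, has no randomised groups at the screening EEG, and has no stated consequence for the mu-symptom correlations. A condition-specific occipital change common to all arms would go undetected and unadjusted.

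That much follows from the text alone. The size does not: the range of 0.06 to 0.28 and all the simulated rates rest on assumed correlations, SD, leakage and n, and show direction only. At the low end the effect is minor; at the high end a false biomarker finding would be common. The documents do not establish that contamination is present, or that the result would be reported as mu-specific.

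The impact is confined to Aim 7 and the EEG secondary objectives. The PANSS primary analysis is unaffected.

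**What to change.** 1. In the paradigm description, state the across-condition test: the O1/O2 log ratio against zero within subject, for each experimental condition, at each EEG session. Define the groups, and keep the arm comparison only for the week-6 treatment contrast.
2. Under MU-Suppression, name the central sites and report each central mu-symptom correlation with and without the O1/O2 log ratio from the same session and condition as a covariate, using the same type of coefficient both times. If the predictor is a pre-to-post challenge change, use the corresponding occipital change.
3. State in advance that a correlation which disappears on adjustment will not be described as mu-specific.
4. Separately, the two statements of the challenge dose (footnote k and the Visit 1 description) contradict each other and must be reconciled.

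The cost is analysis-plan wording and one degree of freedom, since the occipital ratio is already computed. The real downside is lost power if O1/O2 carries true mu (0.30 falling to about 0.22 in the example above). That is why both results should be reported and neither should replace the other.
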